- Proportion of patients who achieved target level of resting HR (55-60 bpm) at week 12 of prospective observation.
- Correlation between the resting HR values stratified by groups and achievement of BP targets at week 12 of prospective observation .
- Proportions of patients with high, medium or low adherence to the treatment with SPC of bisoprolol/perindopril, assessed by MMAS-8 self-reporting questionnaire at week 4 of prospective observation.
- Proportions of patients with high, medium or low adherence to the treatment with SPC of bisoprolol/perindopril, assessed by MMAS-8 self-reporting questionnaire at week 12 of prospective observation.
- Incidence rate of adverse events/ adverse drug reactions and special situations during 12 week observational period of the study.

2 Methods and documentation

Study design and definitions

This is a multi-centre, observational, incomparative, ambispective study, which will retrospectively and prospectively collect clinical and socio-demographic data from medical records of patients with HTN and previous MI initiated with bisoprolol/perindopril SPC in real clinical settings.

Baseline data will be collected retrospectively from medical records of patients with HTN and a history of MI. Baseline data are defined as clinical parameters of interest available in medical records at the nearest date before or at the date of the initiation of SPC with Bisoprolol/ Perindopril.

To be included in the study for further prospective observation a patient should have been administered bisoprolol/ perindopril SPC within first three months before the Index Date. (*Fig.1*).

The Index date is a date when a decision to include a patient in the study for further 12 week prospective observation made by a treating physician after evaluation of recorded data to confirm patient's eligibility for the study.

Therefore, criteria for non-inclusion or inclusion of patients in the study are to be retrospectively evaluated by the treating physician using recorded clinical data available from medical records. Once a treating physician makes decision to include a patient in the study and, in particular, on the prospective observation for 3 months, a visit 0 (inclusion visit) to the clinic for obtaining signed patient's consent to participate in the study should be appointed and made within 1 month from the Index Date.

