Retrospective screening and evaluation of patient's eligibility to inclusion/ exclusion criteria for entering the study allows mitigating a potential risk of deliberative medicine administration within the observational program. Such studies are carried out in case of observational programs when the studied drug is administered in line with indications according to the instruction for its medical use.

Several multicenter, non-interventional, open, incomparable studies have been performed with bisoprolol/perindopril SPC in patients with HTN and coronary heart disease (3,8,13,14). A total of 70 general practitioners and cardiologists from primary care facilities will participate in the program. Each doctor will include about 7-8 patients. In total, it is planned to include at least 500 patients.

Calculation of the sample size

As the present research has an exploratory nature, the study is not intended to prove any hypothesis. In this case, a formal calculation of the sample size is not performed. Moreover, all statistical tests will be performed at a level of statistical significance of 0.05 and a power of 80%.

Given that the study will include patients with any grade HTN, the variability of SBP and DBP levels may be high enough. However, assuming that standard deviations (SDs) at baseline does not exceed 50 mm Hg, a sample of 500 patients will allow achieving a statistically significant difference in BP reduction after 3 months of treatment with bisoprolol/perindopril SPC compared with baseline levels, providing it is 6.3 mm Hg or more.

This non-interventional study has an exploratory nature, so the sample size is not a strict parameter and is recommendatory in nature.

Therefore, in order to obtain a representative population of patients with this particular disease and taking into account the practical aspects of conducting research in daily everyday routine practice, the total sample should consist of at least 500 patients.

Selection of doctors

A total of 70 general practitioners and outpatient cardiologists will participate in this non-interventional study.

Selection of patients

Inclusion criteria

1. Age from 18 to 79 years.
2. Signed informed consent to participate in the study.
3. Stable arterial hypertension with concomitant stable angina pectoris of class I-III according to the Canadian Cardiovascular Society (CCS) classification and a history of myocardial infarction not earlier than 3 months before inclusion in the study

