4. Bisoprolol/perindopril SPC prescription 1-3 months before screening
5. Bisoprolol/perindopril SPC prescription in accordance with Russian SmPC, based on necessity in treatment with bisoprolol/perindopril SPC and separated from the decision to include the patient in the study
6. Clinical parameters of interest (Resting HR; SBP and DBP; frequency of angina attacks per week) are available in medical records for the nearest date before or at the date of the initiation of SPC with Bisoprolol/ Perindopril.

Non-inclusion criteria

1. Hypersensitivity to bisoprolol, perindopril, excipients of the medicine, or other ACE inhibitors.
2. Any contraindication for bisoprolol/perindopril's SPC according to the instruction for medical use
3. CAD, angina pectoris of functional class IV according to the CCS classification (Appendix 1).
4. Chronic heart failure of class III-IV according to the New York Heart Association (NYHA) functional classification of heart failure (Appendix 3).
5. Cerebrovascular diseases (ischemic, haemorrhagic stroke, or transient ischemic attack) within the past 6 months prior to inclusion in the study.
6. A history of revascularization procedure within 3 months prior to inclusion in the study.
7. Hypertrophic obstructive cardiomyopathy.
8. Office BP \geq 180/110 mm Hg on treatment
9. Type 1 diabetes mellitus and decompensated type 2 diabetes mellitus.
10. Bradycardia with a heart rate of less than 60 beats per minute.
11. Atrioventricular block (II-III degree), sinoatrial block, or sick sinus syndrome.
12. Severe bronchial asthma or severe chronic obstructive pulmonary disease.
13. Arterial hypotension (BP less than 100/70 mm Hg).
14. Pregnancy, breastfeeding.
15. Secondary hypertension.
16. Severe decompensated diseases of organs and systems requiring continuous treatment.
17. Current participation in another clinical trial and within 30 days prior to signing informed consent.

Treatment during the study

Treatment with the studied drug

bisoprolol 5 mg + perindopril 5 mg once daily
bisoprolol 5 mg + perindopril 10 mg once daily
bisoprolol 10 mg + perindopril 5 mg once daily
bisoprolol 10 mg + perindopril 10 mg once daily

A minimum dosage may also be prescribed:

bisoprolol 2.5 mg + perindopril 2.5 mg 1 time per day (1/2 tablet of bisoprolol 5 mg + perindopril 5 mg)

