2.7.4 Study procedures and data collection

The plan at each visit during the study is presented in Table 1.

Patients will be provided with the self-observation diaries where they will record the BP values self-measured at home, the number of anginal attacks and the need to use short-acting nitrates.

Table 1 – Plan of visits during the study

Procedures	Screening period (retrospective)	V0 Inclusion visit (month 0)	V1 Follow-up visit (month 1)	V2 Final visit (month 3)
Obtaining patient informed consent		×		
Inclusion/ non-inclusion criteria	×	×		
Demographic data		×		
Risk factors and lifestyle		×		
Medical history		×		
Medical records on Resting HR; SBP and DBP; frequency of angina attacks per week for the nearest date before or at the date of the initiation of SPC with Bisoprolol/ Perindopril		×		
Physical examination and vital signs (rest heart rate and BP) at the office visit		×	×	×
Current symptoms and the use of short-acting nitrates		×	×	×
Number of angina attacks per week		×	×	×
Current use of antianginal agents		×	×	×
Current use of other cardiovascular drugs		×	×	×
Current use of other drugs		×	×	×
Treatment adherence assessed by the patient (Morisky Medication Adherence Scale)		×	×	×
Current use of bisoprolol/perindopril SPC and reasons for discontinuation/ disruption of the treatment (if applicable)		×	×	×
Bisoprolol/perindopril SPC dose adjustment and reasons Bisoprolol/perindopril SPC dose adjustment		×	×	×
Adverse events/drug reactions/special situations		×	×	×

COLLECTION DATA:

2.7.4.1. Data evaluation during the screening period:

HCPs participating in the study will conduct a retrospective analysis of patient's records for the purpose of evaluating patient's eligibility to be enrolled in the study. Patients with HTN and a

history of MI, who had been initiated with bisoprolol/perindopril SPC within first three months before the Index Date (see a definition in Study Design and definitions of Section 2) and who meet other inclusion / non inclusion criteria will be included in the study if they sign a consent form at the inclusion visit.

2.7.4.1. Data collection at the inclusion visit (V0):

- Obtaining patient informed consent;
- Checking for inclusion/non-inclusion criteria;
- Physical examination and vital signs;
- Current status of taking bisoprolol/perindopril SPC and a dose regimen;
- Number of weekly angina attacks;
- Current symptoms and the use of short-acting nitrates;
- Current use of antianginal agents;

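### Inclusion criterion 3 literally admits only infarctions in the 3 months before inclusion; neither the intended window nor the anchor date is settled, and no numbered criterion puts the infarction before the start of the study drug

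*Combined protocol and SAP*

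**What the plan says.** All references are to the combined protocol and SAP.

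- **MI window and angina.** Inclusion criterion 3 (section 2, Selection of patients) opens with "Stable arterial hypertension with concomitant stable angina pectoris of class I-III" and ends with "a history of myocardial infarction not earlier than 3 months before inclusion in the study". No other visible text restates the window. The aim and the design text speak only of a previous MI or a history of MI.
- **Revascularisation.** Non-inclusion criterion 6 excludes "A history of revascularization procedure within 3 months prior to inclusion in the study".
- **SPC start.** Inclusion criterion 4 requires "Bisoprolol/perindopril SPC prescription 1-3 months before screening". Study design and definitions is looser and accepts a start at any time in the 3 months before the Index Date.
- **Meaning of inclusion.** Study design and definitions makes the Index Date the day on which the physician decides to include the patient, and says that V0 is to be "made within 1 month from the Index Date". Section 2.7.2 calls V0 the inclusion visit, and section 2.7.4.1 says that eligible patients "will be included in the study if they sign a consent form at the inclusion visit". Criterion 3 does not say which date it counts from.
- **Order.** The design section describes "patients with HTN and previous MI initiated with bisoprolol/perindopril SPC in real clinical settings". Section 2.7.4.1 describes patients with a "history of MI, who had been initiated with bisoprolol/perindopril SPC within first three months before the Index Date".
- **Baseline and outcome.** Baseline is the record closest to SPC initiation, on or before that day. The primary outcome is the change in systolic and diastolic pressure from that record to week 12. There is no comparator.

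**The concern.** An MI that may not be earlier than inclusion minus 3 months must lie within the last 3 months. Any revascularisation for that MI would then fall inside the period barred by non-inclusion criterion 6, and the patient's angina must already count as stable. The opposite reading, an MI at least 3 months old, selects an almost disjoint population. The two readings share only patients with an MI at exactly 3 months or with MIs on both sides of that point. About 70 doctors apply the rule themselves from their own records, so different readings could divide the sample by doctor.

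The second issue is order. Under the literal window, a qualifying MI may fall after SPC start and so after the baseline record. The MI and the care that follows it would then be part of the change in blood pressure, heart rate and angina frequency that the study reports. There is no control group against which to separate them.

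**Working it through.** The plan gives no figure on this point. Its only computed figure, the detectable difference of 6.3 mm Hg, does not enter. The check is date arithmetic in months.

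**Inputs**
- Index Date = 0.
- SPC start S lies in [-3, -1] (inclusion criterion 4).
- V0 lies in [0, +1] (Study design and definitions).
- M is the MI date, A is the date meant by inclusion, and L = A - S is the time from SPC start to A.

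**Assumptions.** Screening takes place on the Index Date, and the prescription date is the date of SPC start. The documents state neither.

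**Range of L**
- Index Date anchor: L runs from 0 - (-1) = 1 to 0 - (-3) = 3.
- V0 anchor: L runs from 0 - (-1) = 1 to 1 - (-3) = 4.

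**Literal window.** M lies in [A - 3, A]. An MI before SPC start needs M ≤ S = A - L. The room for it is therefore max(0, 3 - L) months, and the share of the 3-month window after SPC start is min(1, L/3).

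| Anchor | L | Room before SPC start | Share after SPC start |
|---|---|---|---|
| Index Date | 1 | 2 months | 33% |
| Index Date | 2 (mid-range) | 1 month | 67% |
| Index Date | 3 | 0 | 100% |
| V0 | 1 | 2 months | 33% |
| V0 | 2.5 (mid-range) | 0.5 month | 83% |
| V0 | 3 to 4 | 0 | 100% |

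With the Index Date anchor the room vanishes only at an SPC start of exactly 3 months. With the V0 anchor it vanishes over the whole range of 3 to 4 months. If the MI must also be on record by the Index Date (M ≤ 0), the V0 mid-range share (S = -2, V0 = 0.5) is 2/2.5 = 80%.

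**Opposite reading.** M ≤ A - 3, so M - S ≤ L - 3.
- Index Date anchor: L is at most 3, so M - S ≤ 0. The MI is always at or before SPC start.
- V0 anchor: the order is guaranteed for L up to 3. At L = 4, M - S ≤ 4 - 3 = 1, so the MI can follow SPC start by at most 1 month.

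**Sensitivity to the looser SPC rule.** If S may lie in [-3, 0], L starts at 0 under either anchor. The literal room is then 0 to 3 months and the share after SPC start is 0% to 100%.

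**Revascularisation.** Under the literal window, a procedure for the qualifying MI dates from between M and inclusion, hence within 3 months of inclusion, and non-inclusion criterion 6 applies. A patient with a recent MI, no revascularisation in that time and stable angina still meets both rules.

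**The case against.** The best defence has four parts.

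1. **The literal reading is workable and may be intended.** The eligible group under it is narrow but not empty, and the introduction mentions patients with a recent MI. This stands in part. A reader might infer that the criteria contradict each other, and they do not. A reader might equally infer that the rule must mean at least 3 months. The stable-angina and revascularisation rules lean that way, but the introductory sentence leans the other way. It is background on treatment, not eligibility text, so it does not settle the matter either. Figure 1, the study scheme, is not shown here and may show the window or the anchor.

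2. **The worst figures depend on V0.** This stands. It is tempting to treat V0 as the settled point of inclusion, because consent is signed there. But the Index Date is itself defined as the decision to include. The 83% mid-range share, the whole range of SPC starts with no usable MI date, and the 1-month gap under the opposite reading all come from the V0 anchor.

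3. **The order is already implied.** Section 2.7.4.1 treats MI patients started on the SPC as a condition alongside the other criteria. It implies the sequence, but it does not date the MI relative to SPC start, and no numbered criterion does so.

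4. **The study is descriptive and promises no causal estimate.** This is true, and it limits the harm. An MI shortly before baseline would also leave recovery and care in the change, which an order rule would not cure. Still, a described change in patients with a previous MI is hard to interpret if the MI may come after the baseline.

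**Conclusion.** The concern holds as an ambiguity of window and anchor together with an unenforced order. It should be fixed, but it does not by itself invalidate the primary outcome.

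The literal window leaves 0 to 2 months for an MI before SPC start under either anchor, and 33% to 100% of it lies after SPC start. Under the opposite reading the order problem disappears with the Index Date anchor and shrinks to at most 1 month with V0. These results assume that screening is the Index Date and that prescription is SPC start.

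A reader might infer from the percentages that most enrolled patients would have an MI after SPC start. The documents do not support that. The figures are shares of calendar time, and such patients must also have stable angina and no recent revascularisation. The number affected cannot be computed.

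**What to change.** - Reconcile inclusion criterion 3 with the stable-angina requirement and non-inclusion criterion 6, and reword it so that the MI window has one meaning.
- State one anchor, Index Date or V0, for inclusion. This review chooses neither the window nor the anchor. The choice of anchor matters, because it decides whether the residual 1-month gap exists under the opposite reading.
- Add a numbered requirement that the MI date precede both the baseline record and SPC initiation, as the design section and section 2.7.4.1 presuppose. Both parts are needed: the plan sets no limit on the age of the baseline record, so an MI could fall between that record and SPC start.
- Report time from MI to SPC start, so that the reader can judge how much post-MI recovery the change may contain.

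**Cost.** One reworded criterion, one added requirement and one descriptive row. Table 1 already lists medical history at V0. Patients whose MI followed the baseline record or SPC start become ineligible. Their number cannot be computed from the documents. The loss is likely to be larger under the literal window, where an SPC start more than 3 months before V0 would leave no eligible MI date if V0 is the anchor.

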Korenova O.Yu. et al. (2019) evaluated the efficacy of bisoprolol/perindopril SPC in patients with recent acute coronary syndrome (ACS) who underwent endovascular coronary intervention. The study has demonstrated an efficient and optimal in time (within the first 4 weeks) achievement of target levels of SBP, DBP and HR, as well as persistence of the effects after 12 weeks of treatment. Clinical benefits of bisoprolol/perindopril SPC included a significant reduction in the severity and rates of manifestations of chronic heart failure and/or angina pectoris (3).

The data of PRESTOL (2019) study examined the efficacy of bisoprolol/perindopril SPC in 2394 hypertensive patients with CAD and showed significant reductions in HR (target HR \leq 70 beats per minute was achieved in 84.9% of patients) and BP (target BP \leq 140/90 mm Hg was achieved in 86.9% of patients). The treatment was associated with a reduction in the number of angina attacks (from 4.4 to 2.6 per week) and an improvement in the treatment adherence level (up to 66.5% of patients) (8).

SPC of bisoprolol/perindopril with several doses of 5/5, 5/10, and 10/10 mg in one tablet makes possible to individualize therapy and increase treatment compliance, while breakable tablets of 5/5, 5/10 mg combinations provide additional options for dose titration (12).

Aim

This non-interventional, ambispective study was aimed at describing effectiveness, safety, and tolerability of bisoprolol and perindopril SPC in patients with HTN and previous myocardial infarction treated with the SPC for 12 weeks in the real clinical practice. SPC will be used according to the approved instruction for medical use of the medicine.

Primary objectives

- To describe antihypertensive effectiveness (SBP and DBP reduction) of bisoprolol/perindopril SPC in hypertensive patients with previous MI at week 12 of prospective observation.

Secondary objectives

- To describe antianginal effectiveness of bisoprolol/perindopril SPC in hypertensive patients with a history of MI at week 12 of prospective observation.
- To describe a proportion of patients achieving target systolic and diastolic BP levels among hypertensive patients with previous MI during 12 weeks of prospective observation with bisoprolol/perindopril SPC according to the age (as stated in the guidelines “2”)

- To describe mean change in resting HR from BL among study patients at week 12 of prospective observation.

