- To describe a proportion of patients who achieved resting HR less than 60 bpm at week 12 of prospective observation.
- To estimate association between the resting HR and achievement of target level of BP at week 12 of prospective observation.
- To describe adherence to the treatment with bisoprolol / perindopril in hypertensive patients with previous MI during the prospective observational period of 12 weeks.
- To describe the tolerability of treatment with bisoprolol / perindopril in hypertensive patients with previous MI during 12 week prospective observation.

Outcome measures

Primary outcome measure:

- Change in the mean systolic and diastolic BP levels at week 12 of prospective observation compared to baseline among patients included in the study.

Secondary outcome measures:

- Change in mean systolic and diastolic BP levels at week 4 of prospective observation compared with baseline.
- Change in number of angina attacks per week at week 4 of prospective observation compared with baseline.
- Change in number of angina attacks per week at week 12 of prospective observation compared with baseline.
- Proportion of patients who were taking lipid lowering therapy (LLT) at week 12 of prospective observation.
- Proportion of patients receiving LLT who achieved target levels of LDL C at week 12 of prospective observation.
- Proportion of patients who achieved SBP \leq 140 mm Hg and DBP \leq 90 mm Hg at week 4 of prospective observation.
- Proportion of patients who achieved SBP \leq 140 mm Hg and DBP \leq 90 mm Hg at week 12 of prospective observation.
- Proportion of patients younger than 65 who achieved SBP \leq 130 mm Hg and DBP \leq 80 mm Hg at week 4 of prospective observation .
- Proportion of patients younger than 65 who achieved SBP \leq 130 mm Hg and DBP \leq 80 mm Hg at week 12 of prospective observation.
- Proportion of patients older than 65 years who achieved SBP \leq 140 mm Hg and DBP \leq 90 mm Hg at week 4 of prospective observation.

- Proportion of patients older than 65 years who achieved SBP≤140 mm Hg and DBP ≤90 mm Hg at week 12 of prospective observation .
- Changes in the mean heart rate (HR) at week 4 of prospective observation compared with baseline.
- Changes in the mean heart rate (HR) at week 12 of prospective observation compared with baseline.
- Proportion of patients who achieved target level of resting HR (55-60 bpm) at week 4 of prospective observation.

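### The revascularisation exclusion and the angina baseline are anchored to different dates, so some procedures after baseline are permitted and would count in the SPC's antianginal change

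*Combined protocol and SAP*

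**What the plan says.** Non-inclusion criterion 6 excludes "A history of revascularization procedure within 3 months prior to inclusion in the study". Inclusion is not tied to one date. Under Study design and definitions, the Index Date is when the physician decides to include the patient, while V0 is named the inclusion visit and "should be appointed and made within 1 month from the Index Date". Table 1 has the eligibility criteria checked both at retrospective screening and at V0.

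The same design section takes baseline from values "available in medical records at the nearest date before or at the date of the initiation of SPC". Inclusion criterion 6 repeats the rule and names weekly angina frequency among the required parameters. Neither place limits how old the record may be. Inclusion criterion 4 requires "Bisoprolol/perindopril SPC prescription 1-3 months before screening". The design section gives only a three-month maximum before the Index Date, with no minimum.

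A secondary outcome is "Change in number of angina attacks per week at week 12 of prospective observation compared with baseline", with a matching one at week 4. Both serve the secondary objective of describing the SPC's antianginal effectiveness.

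Under 2.7.2, V2 takes place at month 3 after V0, or on SPC withdrawal. Table 1 and the V1 and V2 lists in 2.7.4 cover symptoms, nitrate use, angina count, drugs, adherence and adverse events. Revascularisation is not named. The Statistical analysis section is descriptive and has no rule for patients who have a procedure.

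**The concern.** Revascularisation acts directly on angina frequency. In a single-arm before-after comparison, a procedure between the baseline count and the week 12 count enters the change exactly as a drug effect would, and no comparator absorbs it. The plan evidently means to keep recent revascularisation out, but its window is measured from a different date than the outcome it protects. Where the two dates are far enough apart, the protection fails. After V0 there is none. At stake is how far the reported fall in weekly attacks can be read as describing what happened on the SPC.

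**Working it through.** The plan gives no sample-size or expected-change figure for angina, so there is none to reproduce. Its only such figure, 6.3 mm Hg, concerns blood pressure and has no bearing here.

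**Inputs**

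- Look-back: 3 months before inclusion (non-inclusion criterion 6).
- SPC start to screening: 1-3 months (inclusion criterion 4); 0-3 months to the Index Date by the design section. Screening and Index Date are taken to coincide (assumption).
- Index Date to V0: 0-1 month (Study design and definitions).
- V0 to V2: 3 months (2.7.2).
- Age of the baseline record at SPC start: no limit stated.

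**Time left uncovered before inclusion.** Let L be the months from the baseline record to inclusion. The uncovered time is max(0, L - 3).

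*If inclusion means V0 only.* SPC start to V0 is (1 to 3) + (0 to 1) = 1 to 4 months.

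| L (months) | Uncovered before V0 | V0 to V2 | Total uncovered, of baseline to V2 |
|---|---|---|---|
| 1 | 0 | 3 | 3 of 4 |
| 2 | 0 | 3 | 3 of 5 |
| 3 | 0 | 3 | 3 of 6 |
| 4 | 1 | 3 | 4 of 7 |
| 5 (needs a record older than SPC start) | 2 | 3 | 5 of 8 |
| 6 (needs a record older than SPC start) | 3 | 3 | 6 of 9 |

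The scheduled windows alone therefore leave at most 4 - 3 = 1 month open before V0.

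*If inclusion means the Index Date.* SPC start is at most 3 months earlier, so the scheduled windows leave max(0, 3 - 3) = 0 months open before it. From the Index Date to V2, 3 to 4 months are open.

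*If the look-back is applied at both checks in Table 1.* The two windows together run from 3 months before the Index Date to V0, so everything from SPC start to V0 is covered.

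**A case that passes under every reading.** Suppose the last charted weekly angina count is 4 months before the Index Date, the procedure 3.5 months before it, and SPC start 3 months before it. The procedure lies 3.5 months before the Index Date and 3.5 to 4.5 months before V0, always outside the 3-month look-back. SPC start meets inclusion criterion 4. The baseline count predates the procedure and every later count follows it.

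**A case that depends on the reading.** Suppose SPC start is 4 months and the procedure 3.5 months before V0. This is permitted if the count runs from V0 only. SPC start at 4 months puts the Index Date 1 month before V0, so the procedure is 3.5 - 1 = 2.5 months before the Index Date and is excluded if the count runs from there.

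**Size.** The documents give no procedure rate. For scale only, the Introduction reports a fall from 4.4 to 2.6 attacks per week in an earlier study, that is 4.4 - 2.6 = 1.8. If a procedure removed all 4.4 attacks instead of 1.8 (assumption), the extra fall per affected patient is 4.4 - 1.8 = 2.6. With a proportion p affected, the mean fall is overstated by p × 2.6.

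| p (assumption) | Patients of 500 | Overstatement per week | Share of 1.8 |
|---|---|---|---|
| 1% | 5 | 0.03 | 1.4% |
| 2% | 10 | 0.05 | 2.9% |
| 5% | 25 | 0.13 | 7.2% |
| 10% | 50 | 0.26 | 14% |

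**The case against.** The strongest reply is that criterion 6 mostly works. A reader might infer from the separate anchors that any procedure after baseline slips through. The arithmetic does not support that: baselines up to 3 months before inclusion are fully covered, and the scheduled windows leave nothing open if the count runs from the Index Date or is made at both checks. This stands. What remains before V0 is the older record, plus at most 1 month under the V0-only reading. The older record is partly a matter of the missing age limit, and often the nearest record may be the prescribing visit itself.

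Second, no entry criterion can prevent a procedure after V0, so that gap is not a fault of criterion 6. This also stands. It is a separate matter of recording and analysis.

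Third, some procedures may be captured anyway. Medical history is taken at V0, the Concomitant drugs section says concomitant treatment will be documented, and adverse events are reported with hospitalisation as a seriousness criterion. The CRF itself is not among the documents, so the absence of a field cannot be proved. However, a planned procedure need not be an adverse event, and none of these sources is linked to the angina outcomes.

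Fourth, the outcome is secondary and descriptive, and any concomitant treatment is allowed, so the change could never isolate the SPC's effect. That limits the weight of the point without removing it.

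Two further inferences should be resisted. The Introduction cites a study "in patients with recent acute coronary syndrome (ACS) who underwent endovascular coronary intervention", but those patients had their intervention as part of how they were selected. It says nothing about how often procedures follow the baseline record here. Likewise, the 4.4-to-2.6 fall is background from another study, not a planning value.

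**Conclusion.** The point holds in a limited form. Before V0, a permitted procedure can follow the angina baseline when the record is more than 3 months before inclusion. The scheduled windows add at most 1 month, and only if inclusion means V0 alone. From V0 to V2, 3 months are open for every patient, with no named item and no reporting rule. Such procedures would be counted in the SPC's antianginal change.

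Under the stated assumptions (1-10% affected, all 4.4 attacks removed), the overstatement is about 0.03-0.26 attacks per week, or 1.4-14% of a 1.8 fall. A reader might infer a larger distortion by assuming higher rates; nothing in the documents supports one, and nothing rules it out. The blood pressure primary outcome is not part of this point. It is worth correcting because the remedy is cheap, and because without procedure dates the sponsor could not show how small the effect was.

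**What to change.** 1. Define inclusion as one date, or state that the look-back applies at both the Index Date and V0. Reconcile the minimum time on SPC between inclusion criterion 4 and the design section at the same time.
2. Keep the 3-month look-back and extend criterion 6 to exclude also any revascularisation between the baseline angina record and V0. Uncovered time before V0 then falls from max(0, L - 3) to 0 months, whatever the age of the record.
3. Record at V0, V1 and V2 the date of any revascularisation since the baseline record. The exclusion cannot close the 3 months after V0, so this item is needed as well.
4. Keep the all-patient angina change as the main summary at weeks 4 and 12. Add a sensitivity summary without patients revascularised between baseline and the visit concerned, and report their number. The restricted set should not become the main summary: patients may be revascularised because angina worsened, and dropping them could favour the SPC.

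The cost is a few patients becoming ineligible, one criterion edit, one CRF line and one extra table.
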